3. OBJECTIVES

3.1 Primary Efficacy Objective

Primary outcomes will be changes in LH, FSH, testosterone, estrogen, and quality of life from baseline, 14 weeks ± 7 days and 26 weeks ± 7 days.

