4.2 Duration of Study Participation

Total study duration will be 6 months and subjects will be provided with Natesto for the duration of the study (24 weeks treatment course).

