7.3 Pre-Treatment Procedures and Evaluations

Upon evaluating the inclusion/exclusion criteria, patients will be recruited to the study. Patients will be instructed to stop any use of androgen replacement for 4 weeks prior to first treatment session and refrain from using any other androgen replacement therapy option during the study. After the washout period and before the first treatment session, patients will answer the IIEF-EF and SF-36 questionnaires for baseline evaluation.

7.4 Follow-Up Procedures and Evaluations:

Follow-up visits will be conducted at week 14+/- 7 days and 26+/- 7 days, these visits shall include:

- Measuring IIEF-EF and SF-36 scores of patients at the clinic
- Taking serum FSH, LH, E, and total Testosterone levels
- Semen analysis
- Reporting and recording adverse events at every follow-up visit.

Additional determinations of total serum testosterone will be performed periodically at every follow up visit, beginning one month after initiation of therapy. Additional semen analysis will be performed at weeks 15+/- 7 days and 27+/- 7 days.

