10. STATISTICAL CONSIDERATIONS

10.1 Primary Study Endpoints

The primary endpoint will be change in FSH, LH, Testosterone, and Semen Analysis after 6 months of treatment of Natesto.

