10.4 Statistical Analysis and Power calculation

The average and standard deviation of all relevant variables and baseline characteristics, primary and secondary outcomes will be calculated.

Change in sperm count will be analyzed using the ANOVA and MANOVA. A change in $< \pm 10\%$ will be reject the null hypothesis.

LH, FSH, E and Testosterone levels will be analyzed using one-sample t-test with repeated measures throughout the study.

IIEF-EF and SF-36 questionnaires will be analyzed and compared between the groups according to Fisher's exact test in each of the endpoints. The statistical significance will be set at $P < 0.05$.

Demographic characteristics such as age and testosterone level will be compared between groups A and B using student's test. Other demographic characteristics, such as medical background and risk factors will be compared between these groups using Fisher's exact test.

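### Section 10.4 compares IIEF-EF and SF-36 between groups by Fisher's exact test, but the plan describes one Natesto cohort, so the only inferential questionnaire analysis cannot be carried out as written

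*Combined protocol and SAP*

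**What the plan says.** Section 10.4 gives the questionnaire analysis in one sentence: "IIEF-EF and SF-36 questionnaires will be analyzed and compared between the groups according to" Fisher's exact test, at each endpoint, with significance at P < 0.05. It adds that demographic characteristics "will be compared between groups A and B", by Student's test or Fisher's exact test depending on the variable.

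The only other item in 10.4 that covers the questionnaires is descriptive: "The average and standard deviation of all relevant variables and baseline characteristics, primary and secondary outcomes will be calculated". The remaining tests are assigned elsewhere: ANOVA and MANOVA to sperm count, and for the hormones a method that "will be analyzed using one-sample t-test with repeated measures throughout the study".

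On the role of the outcome, section 3.1 says: "Primary outcomes will be changes in LH, FSH, testosterone, estrogen, and quality of life from baseline", at weeks 14 and 26. Section 10.1 says: "The primary endpoint will be change in FSH, LH, Testosterone, and Semen Analysis after 6 months of treatment". Quality of life is in the first list and not in the second.

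On design, section 4.2 says "subjects will be provided with Natesto for the duration of the study". Section 7.4 describes the follow-up data as "Measuring IIEF-EF and SF-36 scores of patients at the clinic", and section 7.3 provides for a baseline questionnaire after washout and before treatment.

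**The concern.** A between-group test needs at least two groups, and the document describes one. Fisher's exact test needs categories, and the document collects scores. Section 3.1 asks how each man changes from his own baseline, whereas a between-group test asks whether two sets of men differ. Any one of these would make the planned test unsuitable, and all three apply.

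What is at stake is prespecification. To report any inference on the questionnaires, the analyst would have to invent the groups, invent a responder cut-off or substitute another test. Nothing in the plan prevents that choice from being made with the data in view. This is more serious because section 3.1 ranks quality of life among the primary outcomes, and because the disagreement with 10.1 leaves open whether the result would be presented as primary.

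**Working it through.** **1. Is there a second group anywhere in the supplied text?**

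| Section | What it describes |
|---|---|
| 2.1, 2.2 | Hypotheses on sperm count relative to baseline |
| 3.1, 3.2 | Outcomes as changes from baseline at weeks 14 and 26 |
| 4.1 | A total of 40 patients; no arms |
| 4.2 | Natesto supplied to subjects throughout |
| 6.3, 10.3 | 80 men; no arms or allocation ratio |
| 7.1 | A prospective study of Natesto; no control or randomisation |
| 12 | One visit schedule, one drug-dispensing row |
| 10.4 | Groups A and B, undefined |

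Only 10.4 mentions groups, and it does not say what they are.

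**2. Could the groups be visits?** No. Section 10.4 also compares age, medical background and risk factors between A and B, which makes no sense for two time points in the same men. Fisher's exact test also assumes independent samples, and repeated scores from the same men are not independent.

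**3. Could 40 against 80 mean two arms of 40?** Section 4.1 gives 40 as a total and section 6.3 gives 80 as one population. That is an unreconciled conflict, not a definition of arms.

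**4. What does Fisher's test return with one group?** Suppose some cut-off put a of n men in one category. The table is [[a, n − a], [0, 0]]. With row totals n and 0 and column totals a and n − a, only one table is possible. Its hypergeometric probability is C(a, a) × C(n − a, n − a) / C(n, n) = 1. So p = 1 for every a from 0 to n, at n = 40 and n = 80. The odds ratio is 0/0 and undefined. This only illustrates the missing second group; it is not a separate defect.

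**5. What could the same scores support?** The document gives no SD for either questionnaire, so results are in units of the SD of the change scores. The half-width of a 95% confidence interval for mean paired change is t(0.975, n − 1)/√n:

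- n = 40: 2.0227/6.3246 = 0.320 SD
- n = 80: 1.9905/8.9443 = 0.223 SD

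For a paired t-test at two-sided alpha 0.05 (10.4 gives 0.05 but not the sidedness), with complete data and no multiplicity adjustment, the detectable mean change is:

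| Men | 80% power | 90% power |
|---|---|---|
| 40 | 0.454 SD | 0.526 SD |
| 80 | 0.317 SD | 0.367 SD |

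The plan has no figure of its own to reproduce here. Section 10.4 mentions power in its heading but gives no effect size, SD, power or dropout rate.

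**The case against.** The best counter-argument concerns severity. Section 10.1 omits the questionnaires, the formal hypotheses concern sperm count only, and no success rule or sample size depends on questionnaire results. Means and SDs are planned. If 10.1 governs, this is a fault in a non-primary analysis. That is fair as far as it goes, but the document does not say that 10.1 governs, and the test is unusable whatever the outcome's rank.

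Section 3.1 names no instrument. Taking SF-36 as the quality-of-life measure is a reasonable inference; for IIEF-EF the support is weaker, since section 11.5 lists QOL forms in one place and the two surveys in another. This stands, and it is a reason to name the instruments in 3.1.

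The document never calls itself single-arm, and its opening pages were not available. The conclusion is an inference from the sections that would be expected to describe a second arm, none of which does. For that reason the remedy begins by allowing that the groups may exist.

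A between-group test could be applied to categories of change. It would then estimate a difference in change between groups, still not the change that 3.1 asks for.

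Finally, the baseline is not consistently placed. Section 7.3 puts the questionnaires after washout and before treatment; the calendar in section 12 marks them at the week 1 screening visit, with dispensing at week 2. For men who need washout these may differ. This stands and belongs in the correction.

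**Conclusion.** The concern holds and should be corrected before analysis. The questionnaire test in 10.4 is wrong as written, not merely under-described: there is no second group, no categorisation of the scores, and a mismatch with the change from baseline that 3.1 asks for. The practical result is that an outcome listed as primary in 3.1 has descriptive statistics but no usable test or confidence interval. A paired analysis of the planned data would estimate mean change to within about ±0.32 SD (40 men) or ±0.22 SD (80 men). Those figures assume complete data and cannot be put into questionnaire points without an SD. The finding rests on the supplied text containing no definition of groups A and B.

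A lesser point does not affect this conclusion: the hormone method, a one-sample t-test with repeated measures, is workable if it means a test of each man's change from baseline, but the text does not say so.

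**What to change.** 1. If groups A and B exist, define them and how men are assigned to them. If not, delete the group comparisons and the Fisher tests from 10.4, and summarise baseline characteristics descriptively for the single cohort.
2. Specify within-man change from baseline in IIEF-EF and in one named SF-36 score (the plan names none) at weeks 14 and 26. Use a paired analysis, or a mixed model with all available visits, and report mean change with a 95% confidence interval.
3. Reconcile 3.1 with 10.1 on whether quality of life is primary, and state which instrument measures it.
4. Reconcile section 7.3 with the calendar in section 12 so that there is one defined baseline questionnaire.
5. State that the hormone one-sample t-test is applied to each man's change from baseline at each visit.

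The cost is wording and minor analysis work. The questionnaires are already planned at baseline, week 14 and week 26, so no new data collection is needed; item 4 settles when the baseline one is taken.

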11. INVESTIGATORS RESPONSIBILITIES

11.1 Investigator Responsibility/Performance

The investigator (or a person designated by the investigator) should inform the patient of all pertinent aspects of the study, including the written information.

The investigator should provide the patient ample time and opportunity to inquire about details of the study and to decide whether or not to participate in the study. All questions about the study should be answered to the satisfaction of the patient. Neither the investigator, nor the study staff, should coerce or unduly influence a patient to participate or to continue to participate in a study.

11.3 Confidentiality

The identity of the patients in this study will be treated as confidential. Patients eligible to participate in the study following the pre-treatment visit will be assigned a unique patient code. The results of the study, including any other data, may be published for scientific purposes but will not give the patients' name or include any identifiable references to them.

However, any records or data obtained as a result of the patient participation in this study may be inspected by the sponsor, by any relevant governmental agency, by the Hospital Ethics Committee, or by the persons conducting this study, provided that such inspectors are legally obligated to protect any identifiable information from public disclosure, except where disclosure is otherwise required by law or a court of competent jurisdiction. These records will be kept private in so far as permitted by law.

11.4 Informed Consent and Permission to Use Protected Health Information

It is the responsibility of the investigator to obtain written informed consent from each subject participating in this study after adequate explanation, in lay language, of the methods, objectives, anticipated benefits, and potential hazards of the study. The investigator must also explain that the subject is completely free to refuse to enter the study or to discontinue participation at any time (for any reason) and receive alternative conventional therapy as indicated. Prior to study participation, each subject will sign an IRB approved informed consent form and receive a copy of same (and information leaflet, if appropriate).

The investigator or designee **must** explain to the subject before enrollment into the study that for evaluation of study results, the subject's protected health information obtained during the study may be shared with the study sponsor, regulatory agencies, and the IRB. It is the investigator's (or designee's) responsibility to obtain permission to use protected health information per HIPAA from each subject, or if appropriate, the subjects' parent or legal guardian.

11.5 Source Documentation and Investigator Files

The investigator will maintain adequate and accurate records to document the conduct of the study and to ensure that study data can be subsequently verified. These documents will be classified into two separate categories: (1) investigator study file and (2) subject clinical source documents that corroborate data collected on the CRF's. Subject clinical source documents would include hospital/clinic patient records; physician's and nurse's notes; original laboratory, radiology, pathology, and special assessment reports; QOL forms, signed informed consent forms. When the CRF or any form is used as the source document, this will be clearly stated in the investigator study file.

At a minimum, the following be documented in source documents:

- Medical history/physical condition and diagnosis of the subject before involvement in the study sufficient to verify protocol entry criteria.
- Study number, assigned subject number, and verification that written informed consent was obtained (each recorded in dated and signed notes on the day of entry into the study)
- Progress notes for each subject visit.
- Laboratory test results including semen analysis.

- Condition and response of subject upon completion of or early termination from the study.
- IIEF-EF and SF-36 Surveys.

11.6 Recording and Processing of Data

Data for this study will be entered into electronic CRFs in research database (a web-based clinical research management application). A CRF is required for every patient who received any study intervention. The investigator will ensure that the CRF's are accurate, complete, legible and timely. Separate source records are required to support all CRF entries. All corrections to study data will be made by drawing a single line through the information to be corrected without obscuring it. All corrections will be initialed, dated and explained, if necessary. **Do not use "white-out" or obscuring correction tape.**

11.7 Non-Protocol Research

No investigative procedures other than those described in this protocol will be undertaken on the enrolled subjects without the agreement of the IRB.

11.8 Ethics

The investigator agrees to conduct the study in compliance with the protocol, current good clinical practices, and all applicable (local, FDA) regulatory guidelines and standard of ethics

11.9 Essential Documents for the conduct of a clinical trial

Essential documents are those documents with individually and collectively permit evaluation of the conduct of a trial and the quality of the data produced.

The following documents will be on file:

- CV's and license of all investigators.
- IRB documentation/correspondence.
- Documentation of IRB certification.

12. STUDY CALENDAR

| Visit #, Time | Visit 1 (Week 1) Screening | Visit 2 (Week 2) | Visit 3 (Week 6) | Visit 4 (Week 14) | Visit 5 (Week 15) | Visit 6 (Week 26) | Visit 7 (Week 27) |
|--------------------------------------|-------------------------------|---------------------|---------------------|----------------------|----------------------|----------------------|----------------------|
| Medical & Urological History | • | | | | | | |
| Physical Examination & Questionnaire | • | | | • | | • | |
| Informed Consent | • | | | | | | |
| Inclusion & Exclusion Criteria | • | | | | | | |
| Blood Analysis (FSH, LH, T, E) | • | | • (Only T) | • | • (Only T) | • | • (Only T) |
| Semen Analysis | • | • | | • | • | • | • |
| Drug dispensing | | • | | • | | | |

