1.3 Study Rationale

Current advantages to Natesto TM include ease of delivery and decreased risk of the medication being transfer upon skin contact to woman or children.¹¹ Recently Natesto 4.5% NTG (125 uL/nostril, 11.0mg testosterone/dose) TID dosing was shown to also increase serum testosterone while maintaining normal, though decreased, serum levels of LH and FSH.¹⁶ This has the

theoretical benefit of maintaining normal semen parameters while on TRT with Natesto- to date, this theoretical benefit has not been evaluated.

While Natesto has been shown to have positive effects on Testosterone while maintaining LH and FSH, the impact on sperm count has not yet been proven. Past research has shown a marked reduction in spermatogenesis in topical testosterone gel treatment.¹⁷ Natesto™ has the potential to maintain normal spermatogenesis levels via maintenance of FSH and LH levels in the normal range. Our hypothesis is that Natesto™ will significantly increase Testosterone while having no significant impact on FSH, LH, and serum parameters in men with Low testosterone. A proposed mechanism for this is that the TID dosing of Natesto will maintain pulsatile release of GnRH, preventing marked decreases in serum FSH and LH.

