6.2 Exclusion (Eligibility) Criteria

Subjects meeting any of the following criteria will be excluded from the study:

1. History of significant sensitivity or allergy to androgens, castor oil or product excipients.
2. Clinically significant findings in the pre-study examinations including abnormal breast examination requiring follow-up.

3. Abnormal prostate digital rectal examination (DRE) with palpable nodule(s) or I-PSS score > 19 points.
4. Body mass index (BMI) ≥ 35 kg/m².
5. Azoospermia or severe oligospermia (<1 million sperm/cc) on screening semen analysis: no sperm found in direct nor centrifuged semen sample or previous history of vasectomy.
6. Clinically significant abnormal laboratory value, in the opinion of the investigator, in serum chemistry, hematology, or urinalysis including but not limited to:
 - a. Baseline hemoglobin > 16 g/dL
 - b. Hematocrit < 35% or > 50%
 - c. PSA > 4 ng/mL and age >40
7. History of seizures or convulsions, including febrile, alcohol or drug withdrawal seizures.
8. History of any clinically significant illness, infection, or surgical procedure within 4 weeks prior to study drug administration.
9. History of stroke or myocardial infarction within the past 5 years.
10. History of, or current or suspected, prostate or breast cancer.
11. History of diagnosed, severe, untreated, obstructive sleep apnea.
12. History of abuse of alcohol or any drug substance in the opinion of the investigator within the previous 2 years.
13. History of nasal disorders such as nasal polyps; nasal septal perforation; nasal surgery; nasal trauma resulting in nasal fracture within the previous 6 months or nasal fracture that caused a deviated anterior nasal septum; sinus surgery or sinus disease
14. Donation or loss of 550 mL or more blood volume (including plasmapheresis) or receipt of a transfusion of any blood product within 12 weeks prior to the start of treatment.
15. Inadequate venous access for collection of serial blood samples required for pharmacokinetic profiles.
16. Receipt of any investigational product within 4 weeks or within 5 half-lives prior to the start of treatment.

17. Inability to understand and provide written informed consent for the study.
18. Considered by the investigator or the sponsor-designated physician, for any reason, that the subject is an unsuitable candidate to receive Natesto.
19. History of treatment with clomiphene citrate within the last 12 months.
20. History of varicocele repair.

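### LH and FSH are primary but assayed once per time point, while blood already drawn a week later is tested for testosterone only: a cheap gain in precision is left unused

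*Combined protocol and SAP*

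**What the plan says.** Section 3.1 states: "Primary outcomes will be changes in LH, FSH, testosterone, estrogen, and quality of life from baseline". Section 10.1 states: "The primary endpoint will be change in FSH, LH, Testosterone, and Semen Analysis after 6 months of treatment of Natesto". LH and FSH are in both lists. Section 1.3 offers as a proposed mechanism that "TID dosing of Natesto will maintain pulsatile release of GnRH, preventing marked decreases in serum FSH and LH".

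The calendar (section 12) marks the full panel once at each of Visits 1, 4 and 6 (Weeks 1, 14 and 26). Visit 2 has no blood draw. At Visits 3, 5 and 7 (Weeks 6, 15 and 27) blood is drawn for testosterone alone: "Blood Analysis (FSH, LH, T, E) | • | | • (Only T) | • | • (Only T". Section 7.4 agrees. Its list for the Week 14 and Week 26 visits includes "Taking serum FSH, LH, E, and total Testosterone levels", and the additional determinations it describes are of total testosterone.

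Section 10.4 treats the four hormones alike: "LH, FSH, E and Testosterone levels will be analyzed using one-sample t-test with repeated measures throughout the study". No section provides for replicate or pooled LH/FSH samples. The only mention of serial sampling is exclusion 15 in section 6.2: "Inadequate venous access for collection of serial blood samples required for pharmacokinetic profiles".

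**The concern.** If LH and FSH are released in pulses, as the proposed mechanism implies, one sample reflects the moment of the draw as well as the man's average level. A change computed as one sample minus one sample carries that noise twice. The plan already repeats other measurements a week apart: semen at Weeks 1/2, 14/15 and 26/27, and testosterone at Weeks 14/15 and 26/27. LH, FSH and estrogen have one value per time point, although the tube that could supply a second follow-up value is scheduled. After first dispensing, testosterone has five scheduled values (Weeks 6, 14, 15, 26, 27) and LH/FSH has two (Weeks 14, 26).

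At stake is how precisely the trial estimates the LH and FSH change. Section 1.3 expects no significant impact on these hormones, and it reports that earlier dosing left them normal but lower. A modest fall is therefore a realistic possibility, and the width of the confidence interval around it matters.

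**Working it through.** **The plan's own figure.** None can be reproduced. Section 10.4 has power calculation in its heading but gives no power, effect size or SD. N is 40 in section 4.1 and 80 in sections 6.3 and 10.3, so both are used below.

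**Count from the calendar.** Blood is drawn at six visits (Weeks 1, 6, 14, 15, 26, 27). LH/FSH is assayed at three (Weeks 1, 14, 26), so 3 of 6 draws yield no LH/FSH value.

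**Model.** On the log scale, for n_b baseline and n_f follow-up assays,

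Var(change) = τ² + s²(1/n_b + 1/n_f), with s² = ln(1 + CV²).

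Here CV is the within-man variation of a single LH value and τ is the between-man SD of the true change. Assumed inputs: CV 20% to 40%, τ = 0 unless stated, independent errors, two-sided 0.05. Power uses the noncentral t with N−1 degrees of freedom.

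**Noise variance.**
- Current schedule (1 baseline, 1 follow-up): s²(1 + 1) = 2.0s².
- Paired follow-up (1 and 2): s²(1 + 1/2) = 1.5s², a cut of 25%.
- If the paired errors correlate at ρ, the follow-up term is s²(1+ρ)/2. ρ = 0.3 gives 1.65s² (cut of 17.5%) and ρ = 0.5 gives 1.75s² (cut of 12.5%).
- Paired baseline as well (2 and 2): 1.0s², a cut of 50%. This needs a second pre-treatment sample drawn on study.

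**Worked case, N=80, CV 30%, true fall 10%.** s² = ln(1.09) = 0.0862 and −ln(0.90) = 0.1054.
- Current: variance 0.1724, SE = √(0.1724/80) = 0.0464, noncentrality 0.1054/0.0464 = 2.27, power 0.61.
- Paired follow-up: variance 0.1293, SE 0.0402, noncentrality 2.62, power 0.74.

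**Power, current schedule → paired follow-up, 10% fall**

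| | CV 20% | CV 30% | CV 40% |
|---|---|---|---|
| N=80 | 0.91 → 0.97 | 0.61 → 0.74 | 0.40 → 0.51 |
| N=40 | 0.64 → 0.76 | 0.35 → 0.44 | 0.22 → 0.28 |

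**Less favourable inputs, N=80, CV 30%, 10% fall**
- ρ = 0.3 to 0.5: 0.61 → 0.67 to 0.70.
- τ = 0.2: 0.52 → 0.62.
- τ = 0.4: 0.37 → 0.41.

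**Larger falls, current schedule, τ = 0**
- 20% fall, N=80: 0.997 at CV 30%, 0.95 at CV 40%.
- 20% fall, N=40: 0.91 at CV 30%, 0.71 at CV 40%.
- 30% fall: at least 0.98 at either N for CV 20% to 40%.

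**Is the second draw on treatment?** Section 4.2 gives a 24-week course, and the calendar first dispenses drug at Week 2: 2 + 24 = Week 26. Visit 5 (Week 15) falls within that course. Visit 7 (Week 27) may fall after it.

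**Can paired draws coincide?** Section 7.4 allows ±7 days at each visit. Week 14 plus 7 days and Week 15 minus 7 days overlap, as do Weeks 26 and 27, so a pair could fall on the same day.

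**The case against.** The strongest reply is that the schedule already detects what the plan cares about. The ±10% figure belongs to sperm count (sections 2.1, 2.2 and 10.4). For gonadotropins, section 1.3 speaks of preventing marked decreases, and on the figures above a 20% or 30% fall is seldom missed at N=80. This stands: the gain matters mainly for small falls, or for 20% falls if N is 40 and the CV is high. A reader might infer that the trial cannot detect LH/FSH suppression; the documents do not support that.

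A reader might also infer that single samples tilt the result toward preservation. Random pulse phase adds noise and does not shift the mean change. Reading a non-significant test as preservation would be wrong with any number of assays. That problem comes from having no LH/FSH margin, and extra assays do not cure it.

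The tempting larger figures, a 50% cut in noise variance and power of 0.89 (N=80, CV 30%, 10% fall), cannot be claimed from blood the calendar already schedules. Visit 2 has no blood draw, and section 7.2 reviews the previous month's testosterone from the chart, so one of the two samples in section 6.1, item 4, may predate the study.

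Three smaller points also stand. Section 1.3 calls the pulsatile link a proposed mechanism, not an established fact. The single sample is inferred from one mark per visit and the absence of any replicate rule; the number of tubes or draws is not stated. Week 6 replicates neither follow-up time in section 3.1.

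**Conclusion.** The point holds as a low-cost improvement in precision, not as a flaw that undermines the trial. LH and FSH are primary and measured once per time point, while adjacent follow-up blood is assayed for testosterone only. Pairing the follow-up assays cuts the sampling-noise variance of the change by at most 25%, or 12.5% to 17.5% if paired errors correlate at 0.3 to 0.5. The proportional cut in total variance is smaller where men truly differ in response.

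The gain is secure at Week 14. At six months, the time point named in section 10.1, it depends on whether Week 27 is on treatment; if it is not, Visit 7 gives no on-treatment replicate and no gain there. All power figures rest on an assumed LH CV of 20% to 40% and an illustrative 10% fall. Nothing has been sized for FSH or estrogen. Priority: could be changed.

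**What to change.** 1. In the calendar and section 7.4, assay FSH, LH, T and E on the Visit 5 draw.
2. Reconcile section 4.2 with the calendar to state whether subjects are still on treatment at Week 27. If they are, assay the full panel at Visit 7 too.
3. State a minimum gap between paired draws, so that the ±7-day windows cannot bring them together.
4. In section 10.4, define each man's follow-up LH, FSH and E value as the log-scale mean of the paired draws, and analyse its change from baseline. Average the baseline as well only if a second pre-treatment sample is drawn on study.
5. Optionally, assay the full panel at Visit 3 (Week 6). This would show early suppression beside testosterone in the same blood, but it replicates no primary time point.
6. Separately, reconcile the serial pharmacokinetic samples in exclusion 15 with the calendar, which schedules none.

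Cost: three extra assays (LH, FSH, E) per man per added visit. Visit 5 alone is 3 × 80 = 240 assays at N=80 or 3 × 40 = 120 at N=40. Visits 3, 5 and 7 together are 9 per man. No new visit or venepuncture is needed. A second on-study baseline sample would add three more assays per man and, as the calendar stands, a draw that is not scheduled.
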